8.2.15. Concomitant Medications

Concomitant medication information will be collected and documented at each scheduled clinic visit, beginning at Screening. Any concomitant drugs (prescribed or over-the-counter) used during the course of the study and the reason for their use will be recorded. Information regarding the timing, type, and amount will be recorded in the eCRF.

8.3. Blood Collection Summary

Assuming a patient completes the study, the maximum amount of blood to be drawn at a visit is approximately 12 mL at screening, 24 mL during the 2 PK assessments, and 5 mL during the remaining visits. The total amount of blood to be drawn over the entire study (including the screening visit, treatment period, and post-treatment follow-up period) is approximately 61 mL.

9. ADVERSE EVENT ASSESSMENTS

9.1. Adverse Event Definitions

9.1.1. Adverse Events

An AE is any untoward medical occurrence associated with the use of a drug (investigational medicinal product) in humans, whether or not it is considered related to the drug. An AE can therefore be any unfavorable and unintended sign (including an abnormal laboratory finding), symptom, or disease in a study patient who is administered study drug in this study.

For this protocol, untoward medical occurrences that should be reported as AEs include the following:

- All AEs that are suspected or are not suspected to be due to study drug
- Overdose (administration of a study drug dose >4 times the intended total daily dose level for this protocol [>160 mg/kg/day]) of study drug
- All reactions from medication misuse, abuse, withdrawal, sensitivity, or toxicity
- All reactions that result from medication errors or uses of the study drug outside what is described in the protocol
- Apparently unrelated illnesses, including the worsening of a preexisting illness
- Injury or accidents. Note that if a medical condition is known to have caused the injury or accident (a fall secondary to dizziness), the medical condition (dizziness) and the accident (fall) should be reported as 2 separate AEs. The outcome of the accident (hip fracture secondary to the fall) should be recorded in source documents.
- Abnormalities in physiological testing or physical examination findings that require clinical intervention or further investigation (beyond ordering a repeat [confirmatory] test)
- Laboratory abnormalities that require clinical intervention or further investigation (beyond ordering a repeat [confirmatory] test) unless they are associated with an already reported clinical event. Laboratory abnormalities associated with a clinical event (eg, elevated liver enzymes in a patient with jaundice) should be captured in the source documents. Laboratory abnormalities not requiring clinical intervention or further investigation will be captured as part of overall laboratory monitoring, and should not be reported as AEs.
- A pre-existing condition (eg, allergic rhinitis) must be noted on the appropriate eCRF for Visit 1, but should not be reported as an AE unless the condition worsens or episodes increase in frequency during the AE reporting period. Diagnostic and therapeutic non-invasive and invasive procedures, such as surgery, should not be reported as AEs. However, the medical condition for which the procedure was performed should be reported if it meets the definition of an AE. For example, an acute appendicitis that begins during the AE reporting period should be reported as the AE and the resulting appendectomy should be recorded in the source documents. If a surgical procedure was planned prior to entry into the study, and the surgery is not performed because of a worsening of a baseline condition, this should not be reported as an AE. Note that, as

described in [Section 9.1.2](#), any inpatient hospitalization occurring as the consequence of an AE during the study period should be reported as an SAE.

Each AE is to be classified as serious or non-serious by the Investigator using medical and scientific judgment.

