In patients with DMD, the age at which the earliest sign or symptom of the disease is noted ranges from infancy to approximately 6 years old [Ciafaloni 2009]. Initial signs and symptoms of DMD include lordosis, a waddling gait, and the Gowers' sign (a characteristically abnormal method of rising from a supine to a standing position) [Brooke 1989, McDonald 1995, Boland 1996, Worton 2001]. Inexorable progressive weakness is seen, particularly in the proximal musculature. Ambulation becomes increasingly abnormal. By the age of 8 years, most boys have difficulty rising from the floor and ascending stairs and they often fall while walking. Boys with the disease spend less time walking and walk more slowly than healthy boys [McDonald 2005a], and are significantly less active than normal boys of similar age [McDonald 2002, McDonald 2005b]. By 10 to 14 years of age, most are wheelchair-bound. In ambulatory boys with DMD, the most frequent cardiac abnormality is sinus tachycardia and heart rate variability, occurring from childhood and persisting throughout life [Finsterer 2003, Gulati 2005]. Pulmonary function is usually normal before 10 years of age and is well maintained into adolescence in boys receiving corticosteroids [Mendell 1989, Griggs 1991, Phillips 2001, Tangsrud 2001, Biggar 2001, Biggar 2006]. Later in adolescence, cardiac and diaphragmatic muscles become progressively weaker and patients require treatment for cardiac insufficiency and ventilatory support. Patients usually die of cardiac or pulmonary failure by 15 to 22 years of age [Brooke 1989, McDonald 1995, Simonds 1998, Worton 2001, Eagle 2002].

Presently, ataluren is the only therapy available to restore dystrophin protein production and preserve muscle function. The current standard of care is corticosteroids, which do not address the underlying cause of the disease and are not typically initiated prior to the age of 5 years old.

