3.3. Primary Endpoint

The primary endpoints of this study are:

- Overall safety profile in terms of the type, frequency, severity, timing, and relationship to study therapy of any adverse events (AEs) or abnormalities of physical findings, laboratory tests, or ECGs
- Occurrence of any dose-limiting toxicities (DLTs)
- Drug discontinuations due to AEs
- Serious adverse events (SAEs)

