9.3. Adverse Event Recording

All AEs (both serious and non-serious) that occur in patients during the AE reporting period must be recorded, whether or not the event is considered drug related. In addition, any known untoward event that occurs subsequent to the AE reporting period that the Investigator assesses as possibly related to the investigational drug/product should also be recorded as an AE.

All AEs are to be recorded in the source documents and on the eCRF using concise medical terminology; whenever possible terms contained in Medical Dictionary for Regulatory Activities (MedDRA) should be employed. In addition, the following information should be recorded:

- Indication of whether the event is serious or non-serious (see [Section 9.1.2](#))
- Relationship to study drug (see [Section 9.4](#))
- Severity of the event (see [Section 9.5](#))
- Onset date
- Resolution date, or date of death
- Action taken
- Outcome of the event

Classification of the event as serious or non-serious determines the reporting procedures to be followed.

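### The accident note in Protocol 9.1.1 sends the injury from a fall to source documents and gives it no AE term of its own, although the same bullet lists injuries as reportable AEs

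*Protocol*

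**What the plan says.** Protocol 9.1.1 gives a list of occurrences that are to be reported as AEs. One bullet begins "Injury or accidents. Note that if a medical condition is known to have caused the injury or accident" and goes on to an example in which dizziness leads to a fall. For that case "the medical condition (dizziness) and the accident (fall) should be reported as 2 separate AEs". The note then ends: "The outcome of the accident (hip fracture secondary to the fall) should be recorded in source documents".

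The general recording rule is in Protocol 9.3: "All AEs are to be recorded in the source documents and on the eCRF using concise medical terminology".

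Protocol 3.3 puts these data first among the primary endpoints: "Overall safety profile in terms of the type, frequency, severity, timing, and relationship to study therapy of any adverse events (AEs", together with abnormal physical, laboratory and ECG findings. SAP 12.1.3 summarises AEs by MedDRA system organ class (SOC) and preferred term (PT), with further tables by severity, by relationship, for events leading to discontinuation and for serious events. It plans no table of injuries or of accident outcomes.

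**The concern.** The bullet opens by making injuries reportable and ends by routing the injury in its own example somewhere other than the AE form. A site that follows the example would enter dizziness and fall, and no fracture. A fracture is a medical condition with its own onset, grade, causality and resolution, and it fits the broad AE definition at the top of 9.1.1.

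The type and severity of AEs are named parts of the primary endpoint. If the injury has no AE record, the tables show that a boy fell but not what happened to him as a result. A fall without harm and a fall with a fracture would carry the same preferred term.

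**Working it through.** The point turns on wording, so the texts are compared first. The only arithmetic is a statement of scale. The plan gives no figure on this point to reproduce.

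**1. What the example counts.** Protocol 9.1.1 fixes the number of AEs at two, the causal condition and the accident. The fracture is mentioned after that count and is given a different destination.

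**2. What that destination means elsewhere in 9.1.1.** The same expression occurs twice more:

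| Item in 9.1.1 | What is reported as the AE | What goes to source documents |
|---|---|---|
| Laboratory finding tied to a reported event | The clinical event (jaundice in the example) | The laboratory finding: "Laboratory abnormalities associated with a clinical event (eg, elevated liver enzymes in a patient with jaundice) should be captured in the source documents" |
| Operation for a condition | The condition: acute appendicitis | The operation: "should be reported as the AE and the resulting appendectomy should be recorded in the source documents" |
| Accident | The fall, and its known cause | The fracture |

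In the first two rows the item in the last column is not a separate AE. The natural reading of the third row is the same. The analogy is a poor one, however. An operation is a procedure and a laboratory value is a finding, whereas a fracture is a medical condition in its own right.

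**3. Contrast with 9.3.** For AEs, 9.3 names two destinations, source documents and the eCRF. The accident note names one.

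**4. Conflict.** The note's last sentence disagrees with the opening words of its own bullet and with the AE definition in the same section. The AE definition in SAP 12.1.1 has no exception for the outcome of an accident, so the SAP does not explain the carve-out either.

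**5. Tracing a fracture through to the tables.** Protocol 11.3 builds the by-subject listings from eCRF modules, and SAP 12.1.3 counts subjects by SOC and PT. An injury with no AE entry therefore has no PT. SAP section 5 omits rows in which no subject has an event, so the fracture would be absent from the table and not shown as zero.

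**6. Scale.** Input: n = 12 (Protocol 11.1; section 5.1 says at least 12). Exact (Clopper-Pearson) 95% limits:

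- One fracture: 1/12 = 8.3%. The lower limit solves 1 − (1 − p)^12 = 0.025, so p = 1 − 0.975^(1/12) = 0.002, or 0.2%. The upper limit solves (1 − p)^12 + 12p(1 − p)^11 = 0.025, which gives p = 0.385, or 38.5%.
- None recorded: 0/12 = 0%. The upper limit is 1 − 0.025^(1/12) = 0.265, or 26.5%.

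The SAP plans no confidence intervals for AEs. These limits show how much one patient weighs in a study of this size and do not represent a planned analysis.

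**The case against.** The strongest case against the point has four parts.

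*The exclusion is inferred.* A reader might infer that the protocol sends the injury to source documents and nowhere else. It does not say so. Where 9.1.1 means to exclude something it usually does so expressly, as it does for procedures and for laboratory abnormalities that need no action. The following bullet also makes examination findings that need intervention or investigation reportable, and this could cover a fracture. The note itself is conditional on a known medical cause, so its reach to a simple trip is unclear. All of this stands, and a careful site might well enter the fracture. But the text then gives two answers, and the one in the worked example is the one most likely to be followed.

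*The event is not lost.* A reader might infer that injuries from falls vanish from the AE data. The documents do not support that. The fall is an AE; Protocol 9.5 asks for the highest grade reached in each episode; admission makes it serious; and Table 5 lets the sponsor request source documents for serious events. Drug treatments are recorded with the reason for use, and the follow-up examination covers the musculoskeletal system and extremities. None of these routes restores the injury's preferred term. A grade does not identify the injury. SAP 12.1.3.8 tabulates serious events by SOC and PT, so even an admitted case could appear under the fall. For a fracture treated without admission, 9.1.2 does not count emergency-room observation under 24 hours as serious, and Table 5 asks for CRF entries for non-serious events without a source-document request. SAP 12.5 reports examinations as abnormal by body system, and medication reasons feed no AE table.

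*No decision rule depends on it.* The study is uncontrolled and descriptive, and the two intervals above overlap widely. This is correct and limits the consequence to what the safety tables can show.

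*Other instructions may settle it.* The CRF Completion Guidelines and study manual are not available here. They might already require a separate entry. If so, they would contradict the protocol's example, which would still need correcting.

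**Conclusion.** The sentence is wrong as written. It conflicts with its own bullet, with the AE definition and with Protocol 9.3, and its natural effect is that an injury from an accident has no AE term. What is lost is the type of injury in the SOC/PT, severity and SAE tables. The accident itself is still reported. In a study of 12, one affected boy is 8.3% of the population (exact 95% CI 0.2% to 38.5%), and his fracture would have no row.

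This rests on two assumptions: that sites follow the worked example, and that the completion guidelines do not override it.

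Two further readings are tempting and should not be drawn. First, Protocol 2.1 says of boys with the disease that "they often fall while walking", but it describes this by the age of 8, whereas the trial enrols boys from 2 to under 5. The documents give no fall or fracture rate for that age group, so no expected number of missed injuries can be given. Second, a reader might infer that a bone-safety signal would be hidden, because Protocol 14.1.4 names osteoporosis as a corticosteroid side effect. Protocol 2.1 also says that corticosteroids are not usually started before age 5, and nothing in the documents points to a bone effect of ataluren. The point does not need either argument, because the contradiction applies to an injury at any age and from any cause.

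**What to change.** Replace the last sentence of the note in Protocol 9.1.1 with:

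*Any injury resulting from the accident (eg, a fracture secondary to the fall) is also to be reported on the eCRF as a separate AE, with its own onset date, grade, causality, seriousness and outcome, linked to the accident.*

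Align the CRF Completion Guidelines if they repeat the present rule. No new SAP table is needed, because the injury then enters the existing AE tables. This changes recording and does not touch the management of any patient.

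The cost is one sentence and a few more AE records. The downside is that one accident can be counted under more than one preferred term. The link between the records lets a reader see that they belong to the same accident.

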9.1.2. Serious Adverse Events (SAEs)

An SAE is an untoward medical occurrence or effect associated with the use of a study drug at any dose, regardless of whether it is considered to be related to the study drug, which results in one of the following:

- Death (ie, all deaths on treatment or within 4 weeks after last study drug administration), including deaths due to disease progression. Any death occurring later than 4 weeks following the last dose need not be reported as an SAE unless it is a result of an event that started within the period covered by the on-study definition. The reported AE should be the event that caused the death. In addition, any AE resulting in death that occurs subsequent to the AE-reporting period and that the Investigator assesses as possibly related to the study drug should also be reported as serious.
- Life-threatening AE. This is an event that, in the view of either the Investigator or the sponsor, places the patient at immediate risk of death. It does not include an event that, had it occurred in a more severe form, hypothetically might have caused death.
- Inpatient hospitalization or prolongation of existing hospitalization (eg, excluding hospitalizations for administration of the study drug, procedures required by the study protocol, or dystrophinopathy-related diagnostic procedures; other planned hospitalizations; or hospitalizations related only to progression of disease). Treatments in the emergency room for procedures such as hydration that do not require admitting the patient to the hospital and observational durations in the emergency room for less than 24 hours are not considered serious.
- Persistent or significant disability or incapacity or substantial disruption of the ability to conduct normal life functions, not related to dystrophinopathy.
- Any other medically important event that the Investigator or the sponsor judges to be serious or which is defined as serious by the regulatory agency in the local country. Medical judgment should be exercised in deciding whether a reaction is serious in other situations. Important medical events that do not result in death, are not immediately life-threatening, and do not require hospitalization may be considered serious when, based on appropriate medical judgment, they may jeopardize the patient and may require medical or surgical intervention to prevent any of the outcomes listed above. Examples of such medical events include allergic bronchospasm requiring intensive treatment administration in an emergency room or at home, newly diagnosed malignancy, or blood dyscrasias, or convulsions that do not result in inpatient hospitalization, or the development of drug dependency or drug abuse.
- An event need not be reported as a SAE if it exclusively represents a relapse or an expected change or progression of the baseline dystrophinopathy. This type of event need only to be reported as an AE.

Note that any SAEs occurring after the end of the patient's participation in the study should be reported to the sponsor if the Investigator becomes aware of them.

9.1.3. Unexpected Adverse Events

Unexpected AEs are defined as those events that were not previously reported with study drug as referenced in the most current Investigator Brochure, or that are symptomatically and pathophysiologically related to a known toxicity but differ because of greater severity or specificity. For example, under this definition, hepatic necrosis would be unexpected (by virtue of greater severity) if the Ataluren IB only referred to elevated hepatic enzymes or hepatitis. Similarly, cerebral thromboembolism and cerebral vasculitis would be unexpected (by virtue of greater specificity) if the IB only listed cerebral vascular accidents. "Unexpected," as used in this definition, also refers to an AE that is mentioned in the most current IB as occurring with the class of drugs or as anticipated from the pharmacological properties of the study drug, but is not specifically mentioned as occurring with the medicinal product.

For the purposes of considering expectedness, the Ataluren IB provides a summary of the safety profile of ataluren based on available clinical information (also referred to as the reference safety information).

9.2. Eliciting Adverse Event Information

The Investigator is to report all directly observed AEs and all AEs spontaneously reported by the study patient or parent/guardian in case of a child. In addition, each study patient will be questioned about AEs at each scheduled clinic visit after study drug administration or during any telephone contact with the patient or parent/guardian in case of a child. The type of question asked should be open-ended, eg, "*How has your child been feeling?*" or a similar type of query.

9.3. Adverse Event Recording

All AEs (both serious and non-serious) that occur in patients during the AE reporting period must be recorded, whether or not the event is considered drug related. In addition, any known untoward event that occurs subsequent to the AE reporting period that the Investigator assesses as possibly related to the investigational drug/product should also be recorded as an AE.

All AEs are to be recorded in the source documents and on the eCRF using concise medical terminology; whenever possible terms contained in Medical Dictionary for Regulatory Activities (MedDRA) should be employed. In addition, the following information should be recorded:

- Indication of whether the event is serious or non-serious (see [Section 9.1.2](#))
- Relationship to study drug (see [Section 9.4](#))
- Severity of the event (see [Section 9.5](#))
- Onset date
- Resolution date, or date of death
- Action taken
- Outcome of the event

Classification of the event as serious or non-serious determines the reporting procedures to be followed.

9.4. Describing Adverse Event Relationship to Study Drug

Based on the considerations outlined in [Table 3](#) the Investigator should provide an assessment of the relationship of the AE to the study drug, ie, whether there is a reasonable possibility that the study drug caused the AE.

Table 3: Relationship of Study Drug to Adverse Event

Relationship	Description
Probable	A clinical event in which a relationship to the study drug seems probable because of such factors as consistency with known effects of the drug; a clear temporal association with the use of the drug; improvement upon withdrawal of the drug; recurrence upon rechallenge with the drug; lack of alternative explanations for the event.
Possible	A clinical event occurring coincident with administration of the study drug and which may or may not be explained by concurrent disease or other drugs or chemicals. Information on drug withdrawal or rechallenge may be lacking.
Unlikely	A clinical event with a temporal relationship to the study drug exposure that does not preclude causality but for which there is a clear alternate cause that is more likely to have caused the AE than study drug. Such alternatives include a concomitantly administered drug, the patient's disease state, other medical conditions, or environmental factors.
Unrelated	A clinical event, for which a relationship to the study drug seems improbable because of factors such as inconsistency with known effects of the study drug, lack of a temporal association with study drug administration, lack of association of the event with study drug withdrawal or rechallenge, and/or presence of alternative explanations for the event. Alternative explanations might include a known relationship of the AE to a concomitant drug, medical history of a similar event, the patient's disease state, other medical conditions, or environmental factors.

